⁷ Bloemen, M.C.T., et al., Prevention and curative management of hypertrophic scar formation. *Burns*, 2009. 35(4): p. 463-475.

Protocol version: 5

Template updated 5 Jul 2021

Methods and Measures

Design

This study is a randomized, controlled, within-subject trial examining the effectiveness of KeraStat Gel, as compared to the institutional SOC, Mepilex Ag, in improving wound cosmesis. Once the Investigator has determined the subject is a candidate for inclusion in the study, the subject will be approached about enrolling in this study. A total of 30 burn subjects presenting to the Burn Centers will be enrolled.

Upon presenting to the hospital, potential study subjects will be assessed for inclusion and approached for consent, as appropriate. Once the subject and/or legal guardian has consented to participate in the study, baseline assessments can be completed. We anticipate that the majority of subjects presenting with burns that qualify for inclusion in the study will have at least one night stay in the hospital; however, this is not criteria for inclusion. KeraStat Gel and Mepilex Ag will each be randomized to application on one of two identified burn sites on the subject, Burn A or Burn B. All subjects will have one burned area dressed with KeraStat Gel and a second area dressed with Mepilex Ag per SOC. The Investigator or study staff will initially apply the dressings per a computer-generated randomization scheme. The burn dressed with KeraStat Gel will have a secondary dressing of petrolatum gauze and telfa. For subjects who have more than two burns, all additional burns will be treated according to the physician's discretion. Subjects will be provided with enough KeraStat Gel and KeraStat Gel-related dressing supplies upon hospital discharge to accommodate prescribed dressing changes until their next visit. The Investigator will instruct subjects on dressing changes as required by institutional SOC guidelines and instructions for use of KeraStat Gel prior to discharge. The need to maintain treatment consistency will be stressed; Burn A and Burn B should always receive their designated dressing.

For the first 4 weeks, subjects will have weekly visits with site staff. On days 7 and 21, this visit will be remote. On days 14, and 28, this visit will be an office visit.

[figure not shown]

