During remote visits, adverse event recording will be recorded by the site. If the subject has agreed to the use of the Engage application on their phone, the subject will also complete a pain assessment for each burned area (Burn A and Burn B). For the Engage application, the subject number will be obtained for registration and completion of the e-diary. The subject will set up a personal identification number (PIN) and provide responses to security questions that will be used if they forget their PIN. The e-diaries will be completed via a web application on the mobile phone that is hosted in a database. As a Software-as-a-Service (SaaS) provider of clinical trial software and services, Clinical Ink acts as an agent on behalf of customers to collect Clinical Study Data. With respect to all Clinical Study Data, the collecting and processing of data are governed by the contractual relationship with each customer consistent with the notice provisions specified by the customer in their relationship with the individuals participating in the clinical study.

If the subject agrees to and is able, the subject will capture photographs of the wounds and upload to the MyChart application. Briefly, the subject will obtain the photograph and navigate to the MyChart application utilizing the web-browser on their phone. The subject should then navigate to the “Messaging” center and click “Ask a Question”. From here, the subject selects “New Medical Question.” The subject should choose their study physician and mark a “Visit Follow-Up Question”. They then can attach an image and click send.

During office visits on days 14 and 28, adverse event recording, incidence of infection, assessment of reepithelialization, photography, and a pain assessment will be completed for each burned area (Burn A and Burn B). A \$45 gas card (one per visit) and KeraStat Gel-related dressing supplies will be given to the subject during these visits, as well.

Partial thickness burns that do not require excision and grafting are expected to be fully closed within 21 days. Thus, after assessment at discharge, subjects will be followed bi-weekly until 4 weeks post-burn to ensure appropriate healing. Then, subjects will be seen at 3 months (± 7 days), 6 months (± 7 days), and 1 year (± 14 days) post-enrollment for site photographs and in order to assess the development of scarring using the Patient and Observer Scar Assessment Scale (POSAS), and TEWL measurements.

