At baseline, demographic and medical history will be collected, and inclusion/exclusion criteria will be confirmed. If the subject meets these criteria, vital signs will be collected, and the wounds will be randomized to treatment including KeraStat Gel dressings or SOC. Two burns identified by the Investigator will be labeled Burn A and Burn B by study staff and noted on the Case Report Form (CRF). The randomization scheme will be generated in nQuery Advisor 7.0 in advance by the study statistician. An adequate, sequentially numbered, opaque, sealed envelope set will be produced prior to the implementation of the protocol for the site to use. These envelopes will be shipped and maintained at the site with the trial staff member designated by the Investigator or the Investigator themselves to conduct randomization. The staff will choose the first envelope in sequence, record the subject ID and date of the randomization on the outside of the envelope. They will open the envelope and reveal the index card with the treatment assignment for Burn A and Burn B, record again the Subject ID and randomization date on that card, and then upload a photo of the completed card with the Subject's source documentation for the clinic visit. No subject may be randomized early into the study. All envelopes at each site must be used in sequential order. Any alterations to this procedure will be considered a protocol violation. Burns will be examined and photographed. The subject will be asked to complete the Visual Analog Scale (VAS) pain score for each burn site on study. Once each treatment is applied, the subject will once again complete the VAS pain score for each burn site. Thus, two VAS pain scores will be collected for each burn at each treatment application by study staff.

Hospital staff will change dressings until the subject is discharged from the hospital. At discharge, the burns will once again be examined and photographed. The subject will be asked

Protocol version: 5

Template updated 5 Jul 2021

to complete the Visual Analog Scale (VAS) pain score for each burn site on study. Once each treatment is applied, the subject will once again complete the VAS pain score for each burn site. Subjects will be provided with enough KeraStat Gel-related dressings to last 17 days. Subjects will be instructed on dressing changing procedures for both burns per institutional SOC guidelines.

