Dressings will be changed per institutional SOC guidelines but at a minimum of every 3 days. Subjects will return to the clinic on days 14 ± 3 and 28 ± 3 post-enrollment for the first 4 weeks and at months 3 (± 7 days), 6 (± 7 days), and 12 (± 14 days) post-enrollment. Subjects will also participate in a remote visit on days 7 ± 3 and 21 ± 3 post-enrollment. Dressing changes will be continued until reepithelialization is achieved. During each visit, study staff will document the number of dressing changes that occurred outside of clinic visits as well as any pertinent information related to the dressing changes. During visits when dressing changes are still necessary, subjects will complete the VAS pain score before and after dressing changes to each burn, and any unanticipated adverse events related to the device will be logged. Subjects who are able and willing will download an application on their smartphone that will prompt them to record the VAS pain score before and after dressing changes will complete this during remote visits on days 7 and 14. Subjects will also be asked to upload photos of the burns at days 7 and 21 utilizing the medical center's MyChart application. Appearance of the sites will be assessed at months 3, 6, and 12 using the POSAS. During the visits at 3, 6, and 12 months, sites will be subjected to 3 measurements of TEWL. Photographs will be obtained at all in-person visits and may be subjected to wound closure and percent epithelialization measurements via ImageJ. Recording of adverse events (AE), measurement of vital signs, examination of the wound/site of wound, and notation of concomitant medication and procedures will also take place during each visit. All measures will be completed if an individual agrees to a final visit after withdrawal from the study.

Masking

This study will be an open-label study.

Schedule of Events

Baseline Testing (All subjects)

- Photographs (prior to start of treatment)
- Vital signs (e.g., blood pressure, heart rate, temperature, height, weight)
- Examination of wound, including wound measurement
- Concomitant medications
- VAS pain score before and after dressing application

Discharge

- Adverse events

- Vital signs
- Examination of wound, including wound measurement and percent reepithelialization
- Photography of treatment site
- Concomitant medications and procedures
- Dressing change
- VAS pain score before and after dressing change

Day 7, 21 (± 3 , Remote visit)

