For the primary objective of the study, improved cosmesis will be analyzed using data from the POSAS, as a total score, and separately for the observer score and then the subject score. Changes from baseline will be examined at 3 months, 6 months and again at 1 year post treatment. TEWL will be considered at 3 months, 6 months, and 1 year. This analysis may also consider the baseline status of the burn including depth, surface area, location of the burn injury and subject baseline characteristics (age, concomitant injury).

Protocol version: 5

Template updated 5 Jul 2021

Secondary objectives include determining whether KeraStat Gel wound dressing results in less painful dressing changes, faster reepithelialization, and reduction in need for excision and grafting. Improvement in pain will be assessed using the scoring from the VAS pain scale at Screening, Days 7, 14, 21 and 28. Box plots of the VAS pain scores will be presented displaying the medians and quartiles in each treatment group over time. A nonparametric test will be used to determine changes in the score across time (Kruskal-Wallis) as well. Reductions in excision and grafting will be analyzed by treatment groups using the same methods as the VAS pain score. Median time to 100% reepithelialization by study treatment group will be conducted, mean times (days) will be analyzed using a Wilcoxon test by treatment groups, as well as a time to event analysis for 90% or higher reepithelialization from baseline.

The incidence of adverse events will be reported and summarized by treatment group. Adverse events will be coded in MedDRA by system organ class and preferred terms (PT).

Human Subjects Protection

Subject Recruitment Methods

Subjects who present at the Burn Center at WF or UMC with qualifying burns as determined by the Investigator will be approached for inclusion in the study by study personnel.

Remuneration

Enrolled study subjects will be provided with one \$45 gas card per visit for office visits on days 14 and 28 and months 3, 6, and 12.

Informed Consent

All subjects must give their informed consent in accordance with the informed consent regulations in Title 21 CFR, Part 50. Each subject over 18 years and subjects under 18 and their legally authorized representative will execute written informed consent (and assent if applicable) before any study procedures are conducted. Study personnel will obtain written informed consent in the clinic.

Confidentiality and Privacy

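### The only test named for dressing-change pain is Kruskal-Wallis across time: it does not compare the two dressings, assumes independent groups, and is carried over to excision and grafting

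*Combined protocol and SAP*

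**What the plan says.** The Design section makes this a within-subject trial: "All subjects will have one burned area dressed with KeraStat Gel and a second area dressed with Mepilex Ag per SOC". The Sample Size entry gives 30 subjects and 60 wounds, with no alpha, SD, correlation or effect size.

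For pain, the Analytical Plan lists VAS scores at Screening and Days 7, 14, 21 and 28, and then gives two items:

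- A display: "Box plots of the VAS pain scores will be presented displaying the medians and quartiles in each treatment group over time".
- A test: "A nonparametric test will be used to determine changes in the score across time (Kruskal-Wallis) as well".

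For surgery it says: "Reductions in excision and grafting will be analyzed by treatment groups using the same methods as the VAS pain score". For healing time it says "mean times (days) will be analyzed using a Wilcoxon test by treatment groups", without stating rank-sum or signed-rank.

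On collection, the Interactions section says: "Thus, two VAS pain scores will be collected for each burn at each treatment application by study staff". The Analytical Plan does not say which of the two scores, or which difference between them, is analysed, and it names no main time point. A separate SAP is promised before database lock, but the document supplied contains no later SAP text.

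**The concern.** There are two separate faults.

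**Wrong contrast.** The objective compares two dressings. The named test has time as its factor, and the dressings meet only in box plots. Pain is likely to fall as burns heal under either dressing, so a significant result would say nothing about KeraStat Gel. A constant advantage for one dressing would leave the test unchanged.

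**Wrong dependence structure.** Kruskal-Wallis assumes independent groups. Here the same burns are scored at up to five time points, and the two burns belong to one person. Reading the test as a comparison by dressing, which the surgery sentence suggests may be the intent, removes the first fault but not the second.

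At stake are the pain and surgery objectives and, if its Wilcoxon test is run as rank-sum, the healing-time objective. Ignoring the pairing gives up the main advantage of a 30-subject within-subject design. The trial is open-label, so choosing the score, visit and test after results are visible would be hard to defend.

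**Working it through.** **Inputs.** From the documents: 30 subjects, one burn per dressing, five listed pain time points. Assumed, because the documents give none: normal scores with total variance 1, two-sided 5% level, and the correlations and effects stated below. The plan has no figure of its own to reproduce beyond 30 × 2 = 60 wounds. Percentages are from simulation (10,000 or more runs per setting) unless marked approximate; repeat runs differed by about one percentage point or less.

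**1. The test as written: five visits, 30 burns, one dressing.** Let ρ be the correlation between visits on the same burn. With flat pain, the statistic behaves roughly as (1 − ρ) times a chi-square on 4 df, so the rejection rate is P(χ²₄ > 9.488/(1 − ρ)).

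- Flat pain: at ρ = 0.3, 9.488/0.7 = 13.55, giving 0.9%. Simulation gives about 1%, and less at ρ = 0.5 and 0.7.
- Pain falling 0.3 SD per visit: the test rejects in 99.4% to 99.9% of runs for ρ from 0.3 to 0.7.

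Adding a constant to every score under one dressing leaves the ranks within that dressing unchanged. Both results are therefore identical whether the dressings differ by 0 or by 1 SD.

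**2. Read as a comparison by dressing, one score per burn.** Let ρ now be the correlation between a subject's two burns. The test assumes the difference in means has variance 2/30, but the true variance is 2(1 − ρ)/30. Its type I error is therefore about 2[1 − Φ(1.96/√(1 − ρ))], which is 5.0%, 1.9%, 0.6% and 0.03% at ρ = 0, 0.3, 0.5 and 0.7. Simulation, with a true difference of 0.5 SD for power:

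| ρ | Kruskal-Wallis type I error | Kruskal-Wallis power | Signed-rank power |
|---|---|---|---|
| 0 | 5.3% | 44–45% | 45% |
| 0.3 | 2.2% | 44–45% | 58% |
| 0.5 | 0.8% | 44–45% | 74% |
| 0.7 | 0.05% | 44–45% | 92% |

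Nothing is lost at zero correlation; the loss grows as the correlation rises.

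**3. Read as a comparison by dressing, five visits pooled as independent.** Let s and b be the shares of variance at subject level and burn level. The true variance of the dressing difference, divided by the variance the test assumes, is 5b + (1 − s − b). With flat pain and no dressing difference:

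| s | b | Ratio | Approximate type I error | Simulated |
|---|---|---|---|---|
| 0.5 | 0 | 0.5 | 0.6% | 0.9% |
| 0.3 | 0.2 | 5(0.2) + 0.5 = 1.5 | 11.0% | 10.7% |
| 0 | 0.5 | 5(0.5) + 0.5 = 3.0 | 25.8% | 26% |

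The direction of error depends on how the test is run and where the correlation lies.

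**4. Excision and grafting.** Suppose 6 subjects are grafted only on the Mepilex Ag burn, none only on the KeraStat Gel burn, and k on both. Exact McNemar uses only the discordant pairs: p = 2 × (1/2)⁶ = 0.031 for every k. Five one-way pairs would give 2 × (1/2)⁵ = 0.0625, so six is the minimum for p < 0.05. For two groups and a yes/no outcome, tie-corrected Kruskal-Wallis is (59/60) times the Pearson chi-square on (6 + k)/30 against k/30:

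| k | Pearson χ² | × 59/60 | p |
|---|---|---|---|
| 0 | 6.667 | 6.556 | 0.010 |
| 3 | 3.750 | 3.688 | 0.055 |
| 6 | 2.857 | 2.810 | 0.094 |

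The verdict changes with subjects who were grafted on both burns, who carry no information on the difference between dressings.

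**The case against.** The strongest reply is that this is protocol-level summary text and that the promised SAP will hold the detail. That is fair for the choice of VAS score, the main time point, the type of Wilcoxon test and the rule for unclosed burns, which are simply unspecified here. It does not cover Kruskal-Wallis across time, which is a stated choice that cannot meet the objective. Nothing supplied shows the SAP correcting it.

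A second reply is that comparison by dressing was intended, since the box plots are by treatment group and the surgery sentence says so too. This is plausible, and it means the missing contrast is certain only for the pain sentence. The independence fault remains under either reading.

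Several limits on the numbers also stand:

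- With one score per burn and positive correlation, the error is lost power, not false claims.
- No text says visits will be pooled, so step 3 is conditional, and its 26% requires two burns on one person to share no variance.
- In step 4, Kruskal-Wallis gives the smaller p-value when k = 0. The case with k = 6 needs 18 of 60 burns grafted, although the Background says such burns typically heal without surgery. A yes/no outcome does not by itself rule out Kruskal-Wallis; the sound objection is the pairing.
- With few grafts, McNemar may be uninformative too.

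Finally, these are secondary endpoints, and the primary cosmesis analysis is not affected.

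**Conclusion.** The concern holds, and the plan should be changed before database lock. Followed as written, the pain analysis cannot support or refute the claim of less painful dressing changes: it would almost always be significant if pain falls with healing and almost never if pain is flat, regardless of any constant difference between dressings. Read generously as a comparison by dressing, it forgoes 13 to 47 percentage points of power (58 − 45 and 92 − 45) at within-subject correlations of 0.3 to 0.7 for an assumed 0.5 SD difference, or can exceed the 5% level if visits are pooled. The wrong contrast and the ignored pairing follow from the documents alone. Every percentage depends on the assumed effect, correlation and normal scores.

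**What to change.** Replace Kruskal-Wallis with a within-subject comparison of the dressings.

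- **Pain, main test.** State which VAS score is analysed, for example after minus before the dressing change, and one main time point. Day 14 is a candidate: among the listed time points it is the first in-clinic visit after Screening, Day 7 scores are optional, and the Design section says "Partial thickness burns that do not require excision and grafting are expected to be fully closed within 21 days". Test the KeraStat Gel minus Mepilex Ag difference with the Wilcoxon signed-rank test.
- **Burns no longer dressed.** State in advance how they are scored, with a sensitivity analysis limited to pairs where both burns are still dressed. The Interactions section makes the score conditional: "During visits when dressing changes are still necessary, subjects will complete the VAS pain score before and after dressing changes to each burn". The Schedule of Events lists it at Days 14 and 28 without that condition. Say which applies.
- **Pain over time.** Use a mixed model with dressing, visit, dressing-by-visit, and random effects for subject and for burn within subject, including the Discharge scores and the optional Day 7 and 21 scores.
- **Excision and grafting.** Use the exact McNemar test.
- **Reepithelialization.** State that the Wilcoxon test is signed-rank, give a rule for burns not closed at the last assessment, and stratify or cluster the time-to-event analysis by subject.

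The cost is SAP wording and a little programming before database lock. No new data or visits are needed.

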Burn injuries are classified based on depth as either superficial, partial thickness, or full thickness. Partial thickness burns involve damage to deeper structures within the skin (below the epidermis) such as blood vessels, nerves, and hair follicles. Typically, partial thickness burns can heal without surgical intervention. However, without proper wound management (if the wound dries out or becomes infected), partial thickness burns can progress to deep partial thickness or full thickness burns. While a number of wound dressings are available for use on partial thickness burns, conventional dressings can adhere to and disrupt the wound surface, require frequent dressing changes (up to twice daily), and demonstrate limited effectiveness for their ability to support initial burn wound healing and prevent long-term scarring^{1,2}.

Impaired healing can lead to scarring, which poses functional, aesthetic, and psychological challenges. The lack of effective scar treatment has resulted in a significant need to develop new solutions to control scar formation, prevent contracture, and improve the quality of life for burn victims. Current treatments designed to prevent hypertrophic scar formation include applying silicone sheets or gels over the burn 14 to 21 days post-injury, occlusive dressings, pressure garment therapy for up to 2 years post-injury, silver sulfadiazine, corticosteroids, and treating

¹ Wasiak J, Cleland H, Campbell F. Dressings for superficial and partial thickness burns. *Cochrane Database of Systematic Reviews* 2008, Issue 4.

² Dorsett-Martin W., Persons, B, Wysocki A, Lineaweaver W. New topical agents for topical treatment of partial-thickness burns in children: A review of published outcome studies. Published online at woundsresearch.com 2008 Protocol version: 5

existing scars with laser ablation or excision^{3,4,5,6,7}. None have shown consistent effectiveness in addressing scarring cosmesis.

Rationale

Ideally, wound dressings for partial thickness burns should absorb fluid, maintain high humidity (i.e., moisture) at the wound site to encourage healing, provide a barrier to prevent infection, and possess mechanical characteristics to accommodate movement¹. Currently, there are several biopolymer wound dressings available that function in this manner. These products include Collatek Hydrogel, Occulus Microcyn Wound Gel, Phytacare Alginate Hydrogel Wound Dressing, and Keratec Wound Dressing.

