KeraStat® Gel is a sterile, non-implantable, water-based gelatinous (hydrogel) wound dressing intended to act as a protective covering in the management of a variety of partial thickness dermal wounds. Keratin is a structural, filamentous protein that, when hydrated, forms a hydrogel that provides coverage and maintains a moist environment for injured skin, similar to collagen and other extracellular matrix molecules used in existing products. Therefore, KeraStat Gel is expected to behave in an equivalent manner to conventional biopolymer wound dressings. ISO 10993 biocompatibility studies and performance testing, both *in vitro* and *in vivo*, indicated that KeraStat Gel is safe and biocompatible. Additionally, two clinical studies support the assertion that the product is non-sensitizing, non-irritating, and does not produce a humoral response. The current study is designed to evaluate the effectiveness of KeraStat Gel in improving scarring cosmesis when topically applied as a primary dressing to human subjects with partial thickness burns. We hypothesize that use of KeraStat Gel, as compared to the standard of care (SOC), will result in improved cosmesis of the healed wounds.

Objectives

The primary objective of the proposed research is to determine whether the use of KeraStat Gel as the primary dressing for partial thickness burns results in improved cosmesis of the healed wounds.

Secondary objectives include determining whether KeraStat Gel wound dressing results in less painful dressing changes, faster reepithelialization, and reduction in need for excision and grafting.

³ Delavary, B.M., et al., Macrophages in skin injury and repair. *Immunobiology*, 2011. 216(7): p. 753-762.

⁴ Tandara, A.A. and T.A. Mustoe, The role of the epidermis in the control of scarring: evidence for mechanism of action for silicone gel. *Journal of Plastic Reconstructive and Aesthetic Surgery*, 2008. 61(10): p. 1219-1225.

⁵ Mustoe, T.A. and A. Gurjala, The role of the epidermis and the mechanism of action of occlusive dressings in scarring. *Wound Repair and Regeneration*, 2011. 19: p. S16-S21.

⁶ Steinstraesser, L., et al., Pressure Garment Therapy Alone and in Combination with Silicone for the Prevention of Hypertrophic Scarring: Randomized Controlled Trial with Intraindividual Comparison. *Plastic and Reconstructive Surgery*, 2011. 128(4): p. 306E-313E.

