Below is a schematic overview of the study.

Optional at-home questionnaire and photographs at virtual visits on weeks 1 and 3

Wound assessments, questionnaires, photographs, TEWL assessment at 3 months, 6 months, 1 year

Setting

This study will be conducted in the Wake Forest (WF) Burn Center and in the University Medical Center New Orleans (UMC). Subjects may continue treatment as inpatients or as outpatients.

Subjects Selection Criteria

- **Inclusion Criteria**

- Males and females, age 6 years and older
- Written informed consent and assent, if applicable (including parent if subject is a minor)
- Presenting with at least two comparable, discrete, and separate partial thickness thermal burns, as determined by the Investigator, measuring 50-1,000 cm² each
- Study wounds identified are partial thickness depth
- KeraStat Gel and Mepilex Ag can be applied to the randomized study burn wounds as definitive care treatment within 72 hours from time of injury
- Overall total body surface area (TBSA) burned < 20%

- **Exclusion Criteria**

- Pregnant or nursing
- Prisoner
- Presence of inhalation injury, as determined by the Investigator
- Injury requiring formal intravenous fluid resuscitation
- Concomitant non-thermal traumatic injuries
- Chronic medical conditions including, but not limited to, documented > renal impairment (Cr > 2.5 mg/dL), hepatic impairment (Total bilirubin > 2.5 mg/dL), thromboembolic disorders, active infection in study wound areas, uncontrolled diabetes (HbA1C > 7%), HIV infection, history of melanoma or systemic malignancy within the last 10 years
- Receiving corticosteroids, immunosuppressive agents, radiation or chemotherapy, topical growth factors, or any other medication the Investigator feels will affect wound healing
- Not expected to live at least 13 months post-burn
- Previously treated with a skin graft at either of the treatment sites

- Chemical or electrical burn
- Proposed study wounds are full thickness
- Any condition the Investigator determines will compromise subject safety or prevent the subject from completing the study

- **Sample Size**
The study size is 30 subjects, two wounds per subject, 30 wounds per treatment cohort resulting in 60 total wounds.

Because this trial is designed to examine long-term outcomes, no interim analyses or stopping rules are planned.

Interventions and Interactions

Intervention: KeraStat Gel

Agent description

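### Excision and grafting is given the VAS pain methods, which either do not compare the dressings or ignore the within-subject pairing

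*Combined protocol and SAP*

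**What the plan says.** The Objectives section lists three secondary aims, ending with "faster reepithelialization, and reduction in need for excision and grafting". For the last of these the whole analysis is one sentence in the Analytical Plan: "Reductions in excision and grafting will be analyzed by treatment groups using the same methods as the VAS pain score".

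The VAS methods, in the same paragraph, are two. The display is: "Box plots of the VAS pain scores will be presented displaying the medians and quartiles in each treatment group over time". The test is: "A nonparametric test will be used to determine changes in the score across time (Kruskal-Wallis) as well". The VAS times are Screening and Days 7, 14, 21 and 28.

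The design is paired. Under Methods and Measures, Design: "All subjects will have one burned area dressed with KeraStat Gel and a second area dressed with Mepilex Ag per SOC". Under Sample Size: "The study size is 30 subjects, two wounds per subject, 30 wounds per treatment cohort resulting in 60 total wounds".

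No section says how excision and grafting is coded. The nearest guide is in Design: "Partial thickness burns that do not require excision and grafting are expected to be fully closed within 21 days". There a burn either needs the procedure or does not. The Background suggests that the procedure will be uncommon: "Typically, partial thickness burns can heal without surgical intervention".

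The Analytical Plan also promises a separate SAP before database lock. It is not in the file.

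**The concern.** The question is whether fewer burns need excision and grafting under one dressing than under the other, in subjects who each have one burn on each dressing. That calls for a comparison of two proportions within pairs. The borrowed methods can be read in two ways, and neither provides it.

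- **Across time.** Kruskal-Wallis over the visits asks whether grafting changes from visit to visit. It does not contrast the dressings, and it treats repeated observations of the same burns as independent.
- **By treatment group.** Kruskal-Wallis between the dressings does contrast them, but as 60 unrelated burns. Its p-value cannot respond to how the burns pair up, and its error rate depends on a correlation it ignores.

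Neither reading gives an estimate of the difference with a confidence interval. Box plots of a 0/1 outcome show little when few burns are grafted. At stake is whether one of the three secondary objectives gets a usable answer.

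**Working it through.** **Inputs.** From the documents: 30 subjects, two burns each, 30 burns per dressing (30 × 2 = 60, consistent), and five VAS times. The plan gives no alpha, power, grafting rate or within-subject correlation, so it has no power figure to reproduce. Assumed here: yes/no coding per burn, two-sided 0.05, no missing data, and the rates and phi correlations shown.

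**Formulas.** On 0/1 data, Kruskal-Wallis is H = [(N − 1)/N] × X², where X² is the ordinary unpaired Pearson chi-square. With b and c discordant pairs and m = b + c, exact McNemar is p = 2·P(Bin(m, ½) ≤ min(b, c)) for b ≠ c. Mid-p subtracts P(Bin(m, ½) = min(b, c)).

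**1. Across time, with identical dressings.** Let each dressing have cumulative grafts of 0, 2, 4, 6, 8 out of 30 at the five times. The mean count is 4 and the overall proportion is 20/150.

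X² = (16 + 4 + 0 + 4 + 16)/(30 × 0.1333 × 0.8667) = 40/3.467 = 11.54. H = (149/150) × 11.54 = 11.46 on 4 df, p = 0.022.

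This holds in each arm with no difference between dressings. Coded instead as new procedures per visit (0, 2, 2, 2, 2), H = 2.10 and p = 0.72. Neither p-value concerns the dressings.

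**2. Two-group reading, 12/30 on SOC v 6/30 on KeraStat Gel.** The pooled proportion is 0.3. X² = 0.2²/(0.3 × 0.7 × 2/30) = 0.04/0.014 = 2.857. H = (59/60) × 2.857 = 2.81 on 1 df, p = 0.094 for every pairing. The paired analysis of the same margins:

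| Discordant pairs | phi | Exact p | Mid-p | Risk difference, points (Tango 95% CI) |
|---|---|---|---|---|
| 9 v 3 | 0.10 | 0.146 | 0.092 | 20 (−2.9 to 41.2) |
| 8 v 2 | 0.27 | 0.109 | 0.065 | 20 (−0.8 to 39.9) |
| 7 v 1 | 0.44 | 0.070 | 0.039 | 20 (1.9 to 38.6) |
| 6 v 0 | 0.61 | 0.031 | 0.016 | 20 (6.4 to 37.3) |

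The last row is the largest phi these margins allow, so it is a best case.

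**3. Type I error**, by exact enumeration of all 30-pair tables:

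| Rates | phi | Kruskal-Wallis | Exact McNemar | Mid-p McNemar |
|---|---|---|---|---|
| 20% v 20% | 0 | 0.049 | 0.022 | 0.041 |
| | 0.3 | 0.020 | 0.015 | 0.035 |
| | 0.5 | 0.007 | 0.008 | 0.024 |
| 10% v 10% | 0 | 0.054 | 0.010 | 0.028 |
| | 0.3 | 0.022 | 0.004 | 0.015 |
| | 0.5 | 0.008 | 0.001 | 0.006 |

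**4. Power**, same enumeration:

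| Rates | phi | Kruskal-Wallis | Exact McNemar | Mid-p McNemar |
|---|---|---|---|---|
| 40% v 20% | 0.5 | 0.34 | 0.49 | 0.63 |
| 20% v 10% | 0.3 | 0.15 | 0.10 | 0.18 |
| 20% v 5% | 0.3 | 0.43 | 0.28 | 0.43 |
| 15% v 5% | 0 | 0.26 | 0.10 | 0.18 |
| 10% v 5% | 0.3 | 0.07 | 0.01 | 0.04 |

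**5. Box plots.** The median is 0 whenever fewer than half the burns are grafted. With up to 6 of 30 grafted, all quartiles are 0 under each of five common quartile definitions; at 7 of 30, under three of the five. From 8 of 30 the upper quartile leaves 0, so the plot is poor but not always blind.

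**The case against.** The sentence says the analysis is by treatment groups, so a dressing comparison was surely intended, and the literal across-time reading may be uncharitable. That is fair, but the intended reading leads to the unpaired test with no estimate.

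The unpaired test does little harm in one direction. At zero correlation its size is close to nominal (0.049 and 0.054), and with positive correlation it is conservative, so it does not produce excess false claims. At 10% v 10% the mid-p test is even further from 0.05. At low rates, which the Background makes likely, the paired test gains little power or loses some; the clear gain is at 40% v 20% with correlation 0.5. All of this stands. The argument for change therefore cannot rest on power or on closeness to nominal size.

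Yes/no coding is inferred. If the team meant the number of procedures or the area grafted, the box-plot point would need reworking, but the across-time and pairing faults would remain.

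Finally, the promised SAP could correct this. It could, but it is not available, and the Analytical Plan does more than leave the method open: it states a rule, and the rule is unsuitable.

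**Conclusion.** The concern holds. Followed as written, the plan gives this secondary objective either no comparison of the dressings or an unpaired p-value without an effect estimate. The across-time fault and the neglect of pairing follow from the text alone.

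The numerical size rests on assumed coding, rates and correlations. In the example with fixed margins, one unpaired p-value of 0.094 stands in for mid-p values between 0.092 and 0.016. Under equal 20% rates, the unpaired type I error falls from 0.049 to 0.007 as correlation rises from 0 to 0.5. The direction is conservative, and pairing can gain, tie or lose power. This should be fixed, although it concerns a secondary objective and not the primary one.

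**What to change.** Replace the sentence on excision and grafting with wording such as:

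> Excision/grafting, classed as yes or no for each burn by one prespecified time point, will be shown as a paired 2×2 table over subjects. The proportion for each dressing and the paired risk difference with a 95% Tango score interval will be reported, with a mid-p McNemar test.

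Drop the box plots and Kruskal-Wallis for this outcome. The team should also:

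- choose the time point now, and without sight of grafting results by dressing. Database lock is the latest possible date, and the trial is open label;
- state whether need means performed or judged necessary, and whether excision and grafting count together;
- keep the interval method named. At 8 v 2 discordant pairs a Wald interval is 20 ± 1.96 × 100 × √(10 − 36/30)/30, or 0.6 to 39.4 points. It excludes zero while mid-p is 0.065;
- for the intention-to-treat population, report how many subjects have unknown status at the time point, and add a sensitivity analysis using last known status.

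**Cost.** One sentence and one table shell. No new data are needed if procedures are recorded per burn. The Schedule of Events lists concomitant procedures without saying so, so the CRF must be checked.

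**Downside.** With few grafted burns the result will often be inconclusive. Mid-p McNemar needs at least 5 discordant pairs for p < 0.05, and all in one direction if there are only 5 (5 v 0 gives 0.031; 4 v 0 gives 0.0625). Exact McNemar needs 6. At correlation 0.3, the chance of 5 or more discordant pairs is 69% at 20% v 10%, 40% at 15% v 5% and 18% at 10% v 5%.
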